10.9. Appendix 9: Prohibited Concomitant Medications That May Result in DDI

Not applicable to this study.

10.10. Appendix 10: Abbreviations

The following is a list of abbreviations that may be used in the protocol.

Abbreviation	Term
A1 to A3	albuminuria (KDIGO albuminuria severity standardization)
Abs	absolute
ADL	activity/activities of daily living
AE	adverse event
AKI	acute kidney injury
ALT	alanine aminotransferase
AST	aspartate aminotransferase
ATTR-CM	transthyretin cardiomyopathy
ATTR-PN	transthyretin polyneuropathy
AUC	area under the concentration-time curve
AUC ₇₂	area under the concentration-time curve from time 0 to 72 hours
AUC _{inf}	area under the concentration-time curve from time 0 to infinity
AUC _{last}	area under the concentration-time curve from 0 to time of last measurable concentration
AUMC _{inf}	area under the first moment curve from zero time to infinity
AV	atrioventricular
AxMP	auxiliary medicinal product
β-hCG	β-human chorionic gonadotropin
BA	bioavailability
BBS	Biospecimen Banking System
BE	bioequivalence
BMI	body mass index
BP	blood pressure
bpm	beats per minute
BUN	blood urea nitrogen
CFR	Code of Federal Regulations
CIOMS	Council for International Organizations of Medical Sciences
CK	creatinine kinase
CKD-EPI	chronic kidney disease epidemiology
C _{max}	maximum observed concentration
CMC	Chemistry, Manufacturing and Controls
CO ₂	carbon dioxide (bicarbonate)
CONSORT	Consolidated Standards of Reporting Trials
COVID-19	coronavirus disease 2019
CRF	case report form
CRO	contract research organization
CRU	clinical research unit
CSR	Clinical Study Report
CT	clinical trial

Abbreviation	Term
CTMS	clinical trial management system
CTIS	Clinical Trial Information System
CV	cardiovascular
DCT	data collection tool
DDI	drug-drug interaction
DILI	drug-induced liver injury
EC	ethics committee
ECC	emergency contact card
ECG	electrocardiogram or electrocardiography
eCrCl	estimated creatinine clearance
eCRF	electronic case report form
EDB	exposure during breastfeeding
E-DMC	External Data Monitoring Committee
EDP	exposure during pregnancy
eGFR	estimated glomerular filtration rate
EU	European Union
EudraCT	European Union Drug Regulating Authorities Clinical Trials (European Clinical Trials Database)
FDA	US Food and Drug Administration
FIH	First-in-human
FSH	follicle-stimulating hormone
F/U	follow-up
G1 to G5	Grade (KDIGO eGFR category standardization)
GCP	Good Clinical Practice
GGT	gamma-glutamyl transferase
HBcAb	hepatitis B core antibody
HBsAb	hepatitis B surface antibody
HBsAg	hepatitis B surface antigen
HCVAb	hepatitis C antibody
HDL	high-density lipoprotein
HIV	human immunodeficiency virus
HR	heart rate
IB	Investigator's Brochure
ICD	informed consent document
ICH	International Council for Harmonisation of Technical Requirements for Pharmaceuticals for Human Use
ID	identification
IMP	investigational medicinal product
IND	Investigational New Drug
INR	international normalized ratio
IPAL	Investigational Product Accountability Log
IPM	investigational product manual
IRB	Institutional Review Board

Abbreviation	Term
IV	intravenous(ly)
KDIGO	Kidney Disease Improving Global Outcomes
k_{el}	first-order elimination rate constant
LBBB	left bundle branch block
LDL	low-density lipoprotein
LFT	liver function test
\log_e	natural logarithm
MQI	medically qualified individual
CCI	
N/A	Not Applicable
NIMP	noninvestigational medicinal product
NOAEL	no observed adverse effect level
PD	pharmacodynamic(s)
PE	physical examination
PI	Principal Investigator
PK	pharmacokinetic(s)
PT	prothrombin time
PVC	premature ventricular contraction
QD	once daily
QTc	corrected QT interval
QTcF	QTc corrected using Fridericia's formula
qual	qualitative
RBC	red blood cell
RNA	ribonucleic acid
SAE	serious adverse event
SAP	Statistical Analysis Plan
SARS-CoV-2	severe acute respiratory syndrome coronavirus 2
Scr	serum creatinine
Scys	serum cystatin C
SoA	schedule of activities
SOP	standard operating procedure
SRSD	single-reference safety document
SUSAR	Suspected Unexpected Serious Adverse Reaction
CCI	
T bili	total bilirubin
THC	tetrahydrocannabinol
CCI	
ULN	upper limit of normal
US	United States
UTI	urinary tract infection
WBC	white blood cell
WOCBP	woman/women of childbearing potential

1. VERSION HISTORY

Table 1. Summary of Changes

Version/ Date	Associated Protocol Amendment	Rationale	Specific Changes
1 07 Jul 2022	Original 19 May 2022	N/A	N/A

2. INTRODUCTION

A 12.2 milligram (mg) tafamidis free acid tablet is being developed to replace the current commercial 20 mg tafamidis meglumine dosage formulation.

[figure not shown]
The purpose of the study is to determine if a 12.2 mg tafamidis free acid tablet (Test) formulation is bioequivalent to the commercial 20 mg tafamidis meglumine soft gelatin capsule (Reference) and to estimate the effect of food on the bioavailability of the 12.2 mg tafamidis free acid tablet.

This SAP provides the detailed methodology for summary and statistical analyses of the data collected in Study B3461103.

2.1. Modifications to the Analysis Plan Described in the Protocol

None.

2.2. Study Objectives and Endpoints

Objectives	Endpoints
Primary:	Primary:

 • To establish the bioequivalence of 12.2 mg tafamidis free acid tablet (Test) and commercial 20 mg tafamidis meglumine soft gelatin capsules (Reference) in fasted healthy participants. 	
 • AUC_{inf} (if data permit, otherwise AUC_{last}) and C_{max} of tafamidis.
Secondary:	Secondary:

 • To estimate the relative bioavailability of a single dose of the 12.2 mg tafamidis free acid tablet administered under fed conditions compared to a single dose of the 12.2 mg tafamidis free acid tablet administered under fasted conditions in healthy participants. 	
 • Not Applicable
CCI	
           	

2.3. Study Design

This study will be a Phase 1, open label, randomized, 3-way crossover, single dose study to determine the bioequivalence of PF-06291826 (tafamidis) 12.2 mg tafamidis free acid tablets versus commercial 20 mg tafamidis meglumine capsules administered under fasted conditions and to estimate the effect of food on the 12.2 mg tafamidis free acid tablet in healthy participants.

A total of 22 participants will be enrolled to ensure a minimum of 18 completers. Participants withdrawn from the study may be replaced. Each period will be separated by a washout of at least 16 days between administration of study drug. Participants will be randomized to receive one of the treatment sequences shown in Table 2:

Table 2. B3461103 Treatment Sequence Schema

Sequence	Period 1	Period 2	Period 3
1 (n=11)	A	B	C
2 (n=11)	B	A	C

A: 12.2 mg tafamidis free acid tablet, fasted (Test)

B: Commercial 20 mg tafamidis meglumine soft gelatin capsule, fasted (Reference)

C: 12.2 mg tafamidis free acid tablet, fed (Test)

3. ENDPOINTS AND BASELINE VARIABLES: DEFINITIONS AND CONVENTIONS

3.1. Primary Endpoints

The primary endpoints are plasma AUC_{inf} (if data permit, otherwise AUC_{last}) and C_{max} of tafamidis administered as 12.2 mg tafamidis free acid tablet and commercial 20 mg tafamidis meglumine soft gelatin capsules, under fasted conditions. Adjusted geometric mean ratios of AUC_{inf} , AUC_{last} and C_{max} will be derived to establish bioequivalence.

In addition, adjusted geometric mean ratios of AUC_{inf} , AUC_{last} and C_{max} of tafamidis administered as 12.2 mg tafamidis free acid tablet under fed conditions, relative to PK parameters under fasted conditions will be derived to estimate the relative bioavailability.

3.2. Secondary Endpoint

Not applicable.

CCI

CCI

Safety and tolerability data will also be evaluated and are discussed in Section 3.5.

3.4 Baseline Variables

Baseline characteristics will be collected according to the schedule of activities (SoA) as specified in the protocol.

3.5. Safety Endpoints

The following data are considered in standard safety summaries (see protocol for collection days, baseline assessment, and list of parameters):

- adverse events (AE)

PFIZER CONFIDENTIAL

- laboratory data
- vital signs data
- ECG results

3.5.1. Adverse Events

Any adverse events occurring following start of treatment will be considered as treatment emergent adverse event (TEAE). Events that occur during follow-up within the lag time of up to 28 days after the last tafamidis dose will be counted as treatment emergent and attributed to the last treatment taken. Events that occur during the washout period (up to 28 days from the last treatment) between study periods will be counted as treatment emergent and attributed to the previous treatment taken. The time period for collecting AEs (“active collection period”) for each participant begins from the time the participant provides informed consent.

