Visit Identifier Abbreviations used in this table may be found in Section 10.10	Screen	Periods 1, 2 and 3									F/U	Early Term Discont	Notes
		Day -1	Day 1	Day 2	Day 3	Day 4	Day 5	Day 6	Day 7	Day 8			
											28-35 days		
 • All screening should be done \leq 28 days before the first dose. • Day relative to start of study intervention (Day 1). • At least a 16 day washout interval between Day 1 in each subsequent period. • Follow-up may occur via telephone contact and must occur 28 to 35 days after administration of the final dose of study intervention.
COVID-19 testing	X	X				X							
 • The testing for COVID-19 pathogen will be performed at each visit per local site procedures. For participants admitted for residence, a subsequent COVID-19 test will be performed after 4 days (ie, upon completion of 4 x 24 hours in house), or if they develop COVID-19 like symptoms.
COVID-19 check temperature	X	X	X	X	X	X	X	X	X				
 • To be done at least daily during residence.
Study intervention administration			X										
 • Participants fasted overnight (minimum of 10 hours) prior to dosing and for 4 hours postdose on Day 1 (Periods 1 and 2 only).
Pharmacokinetic blood sampling			X	X	X	X	X	X	X	X	X		
 • Final visit procedures will be performed on the last day of the last period (Day 8 Period 3), or upon study discontinuation.

PFIZER CONFIDENTIAL

Table 1. Study Schedule of Assessment

Visit Identifier Abbreviations used in this table may be found in Section 10.10	Screen	Periods 1, 2 and 3									F/U	Early Term Discont	Notes
		Day -1	Day 1	Day 2	Day 3	Day 4	Day 5	Day 6	Day 7	Day 8			
CCI													
Serious and non-serious AE monitoring		X	X	X	X	X	X	X	X	X	X		• See Section 8.4.3 for follow-up AE and SAE assessments.
Prior/concomitant medication and treatments		X	X	X	X	X	X	X	X	X	X		
CRU discharge										X			

PFIZER CONFIDENTIAL

Pharmacokinetic Sampling Schema

Visit Identifier	Periods 1-3													Notes				
Study Day	1				2	3	4	5	6	7	8	Early Term/ Discont						
Hours Before/After Dose	0	0.5	1	2	3	4	6	8	12	24	48	72	96	120	144	168		Hour 0 = predose sample collection
Study intervention administration	X																	
PK blood sampling	X	X	X	X	X	X	X	X	X	X	X	X	X	X	X	X	X	

PFIZER CONFIDENTIAL

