6.1. Study Intervention(s) Administered

Eligible participants who continue to meet entry criteria will be admitted to the CRU on Day -1 and will be required to stay in the CRU for 8 overnight stays in each period. All participants will be discharged from the CRU following completion of the discharge evaluation, which includes adverse event monitoring, physical examination (at investigator discretion), vital signs, ECG measurements, and safety laboratory tests.

Study Intervention(s)			
Intervention Name	Tafamidis free acid tablet (fasted)	Tafamidis meglumine soft gelatin capsule (fasted)	Tafamidis free acid tablet (fed)
Arm Name (group of participants receiving a specific treatment or no treatment)	Treatment A	Treatment B	Treatment C
Type	Drug	Drug	Drug
Dose Formulation	Tablets	Softgel capsules	Tablets
Unit Dose Strength(s)	12.2 mg	20 mg	12.2 mg
Dosage Level(s)	1 x tablet	1 x capsule	1 x tablet
Route of Administration	Oral	Oral	Oral
Use	Experimental	Experimental	Experimental
IMP or NIMP/AxMP	IMP	IMP	IMP
Sourcing	Provided centrally by the sponsor Refer to the IPM	Provided centrally by the sponsor Refer to the IPM	Provided centrally by the sponsor Refer to the IPM
Packaging and Labeling	Study intervention will be provided in bottles. Each bottle will be labeled as required per country requirement. The product will be provided as open supplies.	Study intervention will be provided in bottles. Each bottle will be labeled as required per country requirement. The product will be provided as open supplies.	Study intervention will be provided in bottles. Each bottle will be labeled as required per country requirement. The product will be provided as open supplies.
Current/Former Name(s) or Alias(es)	PF-06291826	PF-06291826 / Vyndaqel®	PF-06291826

Study Arm(s)			
Arm Title	Treatment A	Treatment B	Treatment C
Arm Type	Test - fasted	Reference - fasted	Test - fed
Arm Description	Participants will receive a single 12.2 mg	Participants will receive a single commercial 20	Participants will receive a single 12.2 mg

Study Arm(s)			
	tafamidis free acid tablet, fasted	mg tafamidis meglumine capsule	tafamidis free acid tablet, fed
Associated Intervention Labels	Tafamidis 12.2 mg tablets	Tafamidis meglumine 20 mg capsules	Tafamidis 12.2 mg tablets

Study interventions will be supplied by Pfizer as tafamidis 12.2 mg tablets and tafamidis meglumine 20 mg soft gelatin capsules.

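### Adverse events are credited to the most recent dose for up to 28 days, but the next dose can cut the window for Treatments A and B to as little as 16 days while Treatment C, always last, keeps 28

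*SAP*

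**What the plan says.** SAP 3.5.1 contains three statements that bear on this point.

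- A general definition: "Any adverse events occurring following start of treatment will be considered as treatment emergent adverse event (TEAE").
- A rule for the time after the final dose: "Events that occur during follow-up within the lag time of up to 28 days after the last tafamidis dose will be counted as treatment emergent". These events go to the last treatment taken.
- A rule for the time between doses: "Events that occur during the washout period (up to 28 days from the last treatment) between study periods will be counted as treatment emergent". These events go to the treatment taken before the washout.

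The nominal limit is therefore 28 days from dosing for every treatment.

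The dose interval is given as a minimum. SAP 2.3 states: "Each period will be separated by a washout of at least 16 days between administration of study drug". The Schedule of Activities (Protocol 1.3) agrees: "At least a 16 day washout interval between Day 1 in each subsequent period". Neither document gives a maximum.

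The two sequences in Protocol 4.1 and SAP 2.3 are ABC and BAC, so C is always given in Period 3. On the closing contact, Protocol 1.3 says: "Follow-up may occur via telephone contact and must occur 28 to 35 days after administration of the final dose of study intervention". In-clinic observation is the same in every period: participants are "required to stay in the CRU for 8 overnight stays in each period" (Protocol 6.1).

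SAP 6.5.1 leaves adverse-event reporting to the sponsor's reporting standard. The readable text of the SAP gives no common post-dose window and no rate per participant-day.

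**The concern.** In a crossover that credits events to the latest dose, a treatment's window ends at the next dose or at the lag limit, whichever comes first. A and B are always followed by another dose in participants who complete the study, and C never is. Within completers the difference can go in one direction only: the window for C is never the shorter one. Randomisation cannot balance this, because only the order of A and B is randomised.

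What is at stake is how the by-treatment safety tables are read. A and C are the same tablet, fasted and fed. If the C column shows more participants with events, a reader may take this as a tolerability effect of food when part or all of it comes from a longer counting period.

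There is also a smaller wording problem. The general definition has no end point, while the two attribution rules stop at 28 days. An event reported on days 29 to 35 at the closing contact, or after day 28 of a long washout, is treatment emergent under the definition but outside the attribution rules.

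**Working it through.** The plan states no figure that depends on these windows, so there is nothing of its own to reproduce first.

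**Inputs**
- Lag limit: 28 days for all treatments (SAP 3.5.1).
- Dose interval *g*: at least 16 days, no maximum (SAP 2.3; Protocol 1.3).
- Position of C: Period 3 in both sequences (Protocol 4.1; SAP 2.3).
- Planned enrolment: 22 (SAP 2.3).
- Event rate by time since dose: not given in the documents, so it is assumed and shown as a range.

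**Step 1. Window length for a completer**

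Window for A or B = min(*g*, 28). Window for C = 28.

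| Actual interval *g* (days) | A or B | C | Ratio C : A or B |
|---|---|---|---|
| 16 | 16 | 28 | 28/16 = 1.75 |
| 18 | 18 | 28 | 28/18 = 1.56 |
| 21 | 21 | 28 | 28/21 = 1.33 |
| 24 | 24 | 28 | 28/24 = 1.17 |
| 28 or more | 28 | 28 | 1.00 |

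If all 22 completed at the minimum interval, A and B would each have 22 × 16 = 352 participant-days and C would have 22 × 28 = 616.

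**Step 2. Effect on incidence at a 16-day interval, no true treatment effect, constant background rate (assumed)**

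If *p* is the 16-day incidence, the 28-day incidence is 1 − (1 − *p*)^(28/16).

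| 16-day incidence (A or B) | 28-day incidence (C) | Ratio | Expected participants of 22 |
|---|---|---|---|
| 10% | 16.8% | 1.68 | 2.2 vs 3.7 |
| 20% | 32.3% | 1.62 | 4.4 vs 7.1 |
| 30% | 46.4% | 1.55 | 6.6 vs 10.2 |
| 40% | 59.1% | 1.48 | 8.8 vs 13.0 |

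**Step 3. The same comparison if the event rate falls after dosing (assumed)**

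With a rate that halves every *h* days, the ratio of cumulative rates is (1 − 2^(−28/*h*)) / (1 − 2^(−16/*h*)).

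| Half-life *h* (days) | Ratio C : A or B |
|---|---|
| 1 | 1.00 |
| 2 | 1.004 |
| 4 | 1.06 |
| 7 | 1.18 |

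The ratio of incidences is no larger than these values.

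**Step 4. A mixture (assumed)**

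Suppose a fraction *f* of the cumulative rate over 16 days is constant background and the rest has ended by day 16. The ratio of cumulative rates is then 1 + *f* × 12/16, which gives 1.19, 1.38 and 1.56 for *f* = 0.25, 0.50 and 0.75.

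**The case against.** The strongest reply is that the SAP treats all three treatments alike. One nominal limit of 28 days applies to each, and crediting events to the most recent dose is a coherent convention. Sixteen days is a minimum; with longer actual intervals the difference shrinks, and at 28 days it is gone. A participant who stops after A or B also has the full 28 days for that treatment. All of this stands. A reader might infer that the SAP allots A and B only 16 days, and the text does not support that.

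A reader might also infer that the tables for C are bound to be inflated. That needs events on about days 17 to 28 after a single dose, and the documents give no event rate by time. Observation in the unit is equal in all periods, while the extra days under C are covered by a contact that may be by telephone, so calendar days are not days of equal ascertainment. This also stands. Yet a 28-day lag treats those days as countable, and background events in participants who have left the unit need not fade with time since dosing.

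Third, safety is descriptive (Protocol 9.3.2, Safety Analyses), and the secondary objective is relative bioavailability. A reader might carry the concern over to the food-effect conclusion. Nothing supports that: the pharmacokinetic comparison does not use these windows. C is also confounded with Period 3, so equal windows alone would not make C versus A a clean tolerability comparison. This limits what the fix can achieve, but does not justify a second imbalance that can be avoided.

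Finally, the sponsor's reporting standard is not supplied and the adverse-event collection section of the protocol is redacted, so an adjustment there cannot be ruled out. On days 29 to 35, the definition can be read as general and the next two sentences as its limits. That makes the point a matter of wording, and the main finding does not rest on it.

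**Conclusion.** The point holds as a possible imbalance in the descriptive adverse-event tables. For completers, the window for A and B is the shorter of the actual dose interval and 28 days, and the window for C is 28 days. The ratio runs from 1.00 (interval of 28 days or more) to 1.75 (interval of 16 days). At 16 days with no treatment effect, incidence under C is raised by between almost nothing and about 1.7-fold. The lower end assumes that events concentrate in the first days after dosing; the upper end assumes a constant background rate and equal ascertainment throughout. The documents do not say where in this range the study will fall.

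No bioequivalence or food-effect pharmacokinetic conclusion changes. This is an inexpensive improvement to the presentation of safety, not a flaw that threatens the study's objectives.

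**What to change.** - **Common window.** In SAP 3.5.1 and 6.5.1, base the by-treatment adverse-event incidence on one post-dose window that is the same for A, B and C. Two workable choices are dosing to Day 8 discharge, when all periods are observed alike in the unit, or up to 16 days after dosing but before the next dose. Either brings the window ratio to 1.00 for completers.
- **Later events.** Tabulate or list them separately, still credited to the last dose, so that nothing collected is lost.
- **Participant-day rates.** These are an alternative, but they correct fully only if the rate is constant. If it halves every 2 days, the rate for C relative to A or B would be 1.004/1.75 = 0.57, an error in the other direction. The common window is the safer main display.
- **One rule after day 28.** Reword the first sentence of SAP 3.5.1 to agree with the 28-day lag, so that events after day 28, at the closing contact or in a long washout, are all handled the same way.
- **Table note.** State that C was always given in Period 3.

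If the sponsor's reporting standard already provides a common window, a cross-reference is enough. Otherwise the cost is SAP wording and one additional table from data already collected. The drawback is that later events leave the main by-treatment comparison, and more of them do so with the Day 8 cut-off than with 16 days.

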3.5.2. Laboratory Data

Safety laboratory tests will be performed as described in the protocol. To determine if there are any clinically significant laboratory abnormalities, the haematological, clinical chemistry (serum) and urinalysis safety tests will be assessed against the criteria specified in the sponsor reporting standards. The assessment will not take into account whether each participant's baseline test result is within or outside the laboratory reference range for the particular laboratory parameter.

For each period, the baseline measurement is the predose measurement on Day -1.

3.5.3. Vital Signs

Seated blood pressure (BP), pulse rate (PR), and temperature will be measured at times specified in the SoA given in the protocol.

The baseline measurement is the predose measurement on Day 1 Period 1.

3.5.4. Electrocardiograms

QT interval, QTcF, PR, QRS and heart rate (HR) will be recorded at each assessment time indicated in the SoA given in the protocol. QTcF will be derived using Fridericia's heart rate correction formula:

$$\text{QTcF} = \text{QT} / (\text{RR})^{(1/3)} \text{ where RR} = 60/\text{HR} \text{ (if not provided)}$$

The baseline measurement is the predose measurement on Day 1 Period 1.

4. ANALYSIS SETS (POPULATIONS FOR ANALYSIS)

Data for all participants will be assessed to determine if participants meet the criteria for inclusion in each analysis population prior to releasing the database and classifications will be documented per standard operating procedures.

Participant Analysis Set	Description
Enrolled	“Enrolled” means a participant’s, or their legally authorized representative’s, agreement to participate in a clinical study following completion of the informed consent process and randomization/assignment to study intervention. A participant will be considered enrolled if the informed consent is not withdrawn prior to participating in any study activity after screening. Potential participants who are screened for the purpose of determining eligibility for the study, but do not participate in the study, are not considered enrolled, unless otherwise specified by the protocol.
Full analysis set	Example: All participants randomly assigned to study intervention and who take at least 1 dose of study intervention.
Safety analysis set	All participants randomly assigned to study intervention and who take at least 1 dose of study intervention. Participants will be analyzed according to the product they actually received.
PK Concentration	The PK concentration population is defined as all participants who receive at least 1 dose of tafamidis and who have at least 1 measurable concentration of tafamidis.
CCI	

